General (FACT-G) with 27 items and a lymphoma-specific concerns scale with 15 items, each item measured on a 0-4 scale (0=not at all; 4=very much). The FACT-G is a general measure of quality of life of cancer patients containing four subscales: physical well-being, social/family well-being, emotional well-being, and functional well-being. It is widely used in cancer clinical trials and is reliable and valid for general research purposes (33) The additional items of the lymphoma-specific concerns scale were developed to capture items relevant to the QOL of lymphoma patients. The FACT-Lym has been shown in a cohort of non-Hodgkin's lymphoma patients to be easy to administer, reliable, valid, and sensitive to change.(34) The recall period for the FACT-Lym is 7 days. The FACT-Lym will be administered to all willing patients via a paper booklet in clinic at baseline and at 3, 6, 9, 12, 18, 24, 30, 36, 48, and 60 months while the patient remains in the active monitoring phase of the study (on treatment or in observation). The FACT-Lym will be scored according to the published scoring algorithm with the following scale scores computed at each time point: physical well-being (PWB, 7 items, score range 0-28), social/family well-being (SWB, 7 items, score range 0-28), emotional well-being (EWB, 6 items, score range 0-24), functional well-being (FWB, 7 items, score range 0-28), FACT-G total score (PWB+ SWB+ EWB+ FWB, score range 0-108), FACT-LymS score (lymphoma-specific concerns, 15 items, score range 0-60), FACT-Lym total score (FACT-G+ FACT-LymS, score range 0-168), and the Trial Outcome Index (PWB+ FWB+ FACT-LymS, score range 0-116). A clinically meaningful change is defined as 2-3 points in the PWB and FWB (35) 3-7 points in the FACT-G total (35) and 3-5 points in the FACT-LymS (36).

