The primary QOL analysis will be conducted at the time of the primary clinical analysis and will include the baseline, month 3 and month 6 QOL data. Additional analyses will be conducted after patients have been followed for 3 years and for 5 years. The primary analysis will compare the FACT-TOI between arms at the 3 month and the 6 month time points using analysis of covariance adjusting for the baseline FACT-TOI score. Mean FACT-TOI will be graphically presented by arm using a mean plot with standard deviation error bars including all available data with patients according to the randomized treatment assignment. Baseline characteristics will be compared between arms within the subject of patients who provide QOL data at one or more time points using t-tests for continuous variables and chi-squared tests for categorical variables. To assess for selection bias, baseline characteristics for patients who provide QOL data at one or more time points will be compared to patients who do not provide any QOL data using t-tests for continuous variables and chi-squared tests for categorical variables. Subsequent analysis will include comparison of FACT-TOI area-under-the-curve from baseline to 6 months between arms using analysis of covariance adjusting for the baseline FACT-TOI score. Responder-type analysis will also be performed in which the percentage of patients who report a 6-point worsening from baseline at either 3 or 6 months will be compared between arms using a chi-square test . The "responder" definition will be investigated using cumulative distribution curves. Lastly, a

linear mixed-effects model will be used to compare the FACT-TOI over time between arms with the post-baseline FACT-TOI score as the modeled outcome and predictors are baseline FACT-TOI, arm, time (treated as a continuous variable and measured at the planned month of assessment), and treatment-by-time interaction. Similar analyses described for the FACT-TOI will be repeated for the other scale scores, and for all scales after 3 and 5 years of follow-up.

Missing data will be handled in several ways. All analyses will first be completed using all available data, followed by analyses completed using imputed data using the arm minimum followed by the arm maximum. Lastly, we will employ pattern mixture models for longitudinal analyses. Output from all analyses will be compared to assess the degree to which missing data impacts study results.

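### The arm-minimum and arm-maximum imputations for missing QOL push both arms the same way, so they do not bound the effect of missing data on the arm difference

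*Combined protocol and SAP*

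**What the plan says.** Section 16.47 sets out the QOL analysis. The main comparison is stated as "The primary analysis will compare the FACT-TOI between arms at the 3 month and the 6 month time points using analysis of covariance", adjusted for the baseline score. An AUC comparison from baseline to 6 months, a responder comparison and a linear mixed model follow. The outcome is the "Trial Outcome Index (PWB+ FWB+ FACT-LymS, score range 0-116").

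Missing data are handled in three steps:

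- "All analyses will first be completed using all available data".
- Then come analyses on "imputed data using the arm minimum followed by the arm maximum".
- "Lastly, we will employ pattern mixture models for longitudinal analyses". No patterns or offsets are given.

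The stated purpose is: "Output from all analyses will be compared to assess the degree to which missing data impacts study results".

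No run is described in which one arm takes its minimum while the other takes its maximum. Section 16.47 also compares baseline characteristics of patients with and without any QOL data. That looks at who takes part at all, not at whether later missing scores differ from observed ones.

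**The concern.** The quantity of interest is a difference between arms. A sensitivity analysis for missing data should ask how far that difference could move if the unseen scores in one arm were worse, or better, than those in the other. Giving each arm its own minimum lowers both means; giving each its own maximum raises both. Much of the movement can then drop out of the difference.

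The unfavourable case is missing scores that are poor in one arm only. If the available-data, arm-minimum and arm-maximum results then agree, their agreement could be taken as evidence that missing data matter little when it is not. Pattern mixture models could allow arm-specific departures, but the plan confines them to the longitudinal analyses.

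Missing QOL data are likely to be informative at the later time points. Section 16.47 collects FACT-Lym only while the patient is in active monitoring, and Section 13.4 ends that at progression or subsequent lymphoma treatment. The 3- and 5-year repeats of these analyses are the most exposed.

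**Working it through.** **Inputs from the documents.** 58 evaluable patients per arm with 1:1 allocation (Section 16.21); FACT-TOI range 0 to 116 and the two single-value imputations (Section 16.47). The documents give no QOL mean, SD, missing fraction or power, so there is no stated figure to reproduce. Those values are assumed below and varied.

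**Formula.** Let D be the Zevalin (B) mean minus the rituximab (A) mean among observed patients, mA and mB the missing fractions, and iA and iB the imputed values. After imputation

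D* = D + mB(iB − meanB) − mA(iA − meanA).

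In the arm-minimum run both bracketed terms are negative; in the arm-maximum run both are positive. The change in D is zero whenever mB(iB − meanB) = mA(iA − meanA). In a crossed run the brackets have opposite signs and the two shifts add.

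**Hand calculation.** Assume mean 90 in A, observed minimum 55 and maximum 116 in both arms, and mean 90 (D = 0) or 96 (D = 6) in B.

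| D | Missing A / B | Arm minimum | Arm maximum | Crossed runs |
|---|---|---|---|---|
| 0 | 10% / 10% | 0.0 | 0.0 | −6.1 to +6.1 |
| 0 | 20% / 20% | 0.0 | 0.0 | −12.2 to +12.2 |
| 6 | 10% / 10% | 5.4 | 5.4 | −0.7 to +11.5 |
| 6 | 20% / 20% | 4.8 | 4.8 | −7.4 to +17.0 |
| 0 | 10% / 20% | −3.5 | +2.6 | −9.6 to +8.7 |
| 6 | 10% / 30% | −2.8 | +9.4 | −8.9 to +15.5 |

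For example, D = 6 with 20% missing in each arm:

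- arm minimum: 6 + 0.2(55 − 96) − 0.2(55 − 90) = 6 − 8.2 + 7.0 = 4.8
- B minimum with A maximum: 6 + 0.2(55 − 96) − 0.2(116 − 90) = 6 − 8.2 − 5.2 = −7.4

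Unequal observed extremes also matter. With minima of 55 in A and 40 in B and 20% missing in each arm, the arm-minimum run gives 6 + 0.2(40 − 96) − 0.2(55 − 90) = 6 − 11.2 + 7.0 = 1.8.

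**Simulation.** Normal scores limited to 0–116, rituximab mean 85, SD 15, 58 per arm, extremes taken from the observed scores in each arm:

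- 15% missing in each arm, true difference 0: planned runs about 0 and 0; crossed about −9.8 to +9.8.
- 15% missing in each arm, true difference 5: planned runs about 4.8 and 4.2; crossed about −5 to +14. Repeat runs vary by about 0.1.
- 10% and 20% missing, true difference 0: planned runs about −3.4 and +3.0; crossed about −9.9 to +9.6.

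**A case the planned runs miss.** Assume 20% missing in each arm, observed means near 90 (Zevalin) and 85 (rituximab), and Zevalin non-completers scoring 25 points below its completers. The full-sample difference is then about −0.3. Available data give 4.8, the arm-minimum run 4.8 and the arm-maximum run 4.1. The crossed run with Zevalin at its minimum gives −8.1. The three planned estimates agree on a difference that is not there.

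For scale, the responder rule counts "the percentage of patients who report a 6-point worsening from baseline at either 3 or 6 months". That is a within-patient cut-off, not a between-arm margin, so it serves only as a yardstick.

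**The case against.** A reader might infer that the planned runs can never show an effect of missing data on the arm difference, or that they reassure whatever the unseen scores are. The documents do not support that. Each run uses the arm's own extreme and acts only on that arm's missing fraction, so the difference moves when missingness or extremes differ: in the table, +6 becomes −2.8 and +9.4 at 10% and 30% missing. Arms that progress at different rates would plausibly have unequal missingness. The exact cancellation belongs to the balanced case.

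Nor are the outputs automatically reassuring in the balanced case. Single-value imputation inflates the variance. In a simulated ANCOVA with 15% missing per arm, a true difference of 5 and an assumed baseline correlation of 0.6, the standard error rises from 2.4 to about 3.1 (minimum) and 2.8 (maximum). Power falls from roughly a half to roughly a third, and more than half of the trials significant on available data lose significance in at least one planned run. That is a loss of precision, however, and says nothing about how far the difference could move.

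A reader might also infer that the plan will declare QOL robust on this evidence. It says only that outputs will be compared. The pattern mixture models, though unspecified, would draw on the same post-baseline scores, including months 3 and 6.

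Finally, crossed bounds are wide enough that few results would survive them, and the sizes here depend on assumed values. Both points are fair. They favour the tipping-point analysis as the main addition. They do not supply an opposing-direction or arm-specific analysis for the ANCOVA, AUC or responder comparison, and none is written.

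**Conclusion.** The point holds in limited form. The two imputation runs shift both arms the same way and do not bound the effect of missing data on the arm difference. With similar missingness and spread they understate it: about 4.8 and 4.2 for a true difference of 5, against about −5 to +14 crossed, at 15% missing per arm. With unequal missingness they respond but still fall well inside the range: about −3.4 and +3.0, against about −9.9 to +9.6, at 10% and 20% missing with no true difference.

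These sizes rest on an assumed mean, SD, extremes and missing fractions. The direction of the shifts follows from the formula and does not. The conclusion also rests on the natural reading that both arms take the same extreme within a run.

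The stakes are modest. QOL is a correlative objective (Section 2.36) and the primary CR comparison is unaffected, although Section 1.2 does single out QOL improvement as something this trial will test again.

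**What to change.** In the missing-data paragraph of Section 16.47:

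1. For the month 3 and month 6 FACT-TOI ANCOVA, add a delta-adjusted multiple imputation. Impute from baseline score and arm, subtract a shift from the imputed values, vary that shift separately in each arm over a pre-stated grid, and report the combinations at which the conclusion changes.
2. Add two crossed runs: Zevalin at its minimum with rituximab at its maximum, then the reverse. Label them as extreme outer bounds, valid if the unseen scores lie within each arm's observed range.
3. Carry the same imputed data sets into the AUC and responder comparisons.
4. State the patterns and offsets for the pattern mixture models, and report the number of missing scores by arm and visit beside every sensitivity result.

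The existing minimum and maximum runs can stay, described as same-direction runs. The cost is a little programming, with no new data, visits or patients. The one drawback is that the crossed bounds will look wide, so interpretation should rest mainly on the tipping point.

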16.25 Accrual Rate and Study Duration: The anticipated accrual rate is 4 patients per month. This study is expected to accrue in ~2.75 years. The total study duration is expected to be approximately ~3.25 years, or until the last patient accrued has been observed for at least 6 months.

16.3 Secondary Outcome Analyses: The secondary endpoints listed below will be evaluated in each arm independently and will also be compared between the two arms. Analysis of all endpoints will occur at the time of the primary analysis (after all patients have completed the 6-month disease assessment), after all patients have been followed for 3 years, and after all patients have been followed for 5 years. For all secondary endpoints, p-values <0.001 will be considered statistically significant at either of the first two analyses. At the 5-year analysis, p-values <0.05 will be considered as statistically significant. P-value boundaries are based on the Haybittle-Peto rule.(31, 32) A final analysis for the purpose of providing updated descriptive estimates may be undertaken after all patients have been followed for 10 years.

16.31 Progression-free survival (PFS) is defined as the time from registration to the earliest date documentation of disease progression or death due to any cause. The distribution of progression-free survival time will be estimated using the method of Kaplan-Meier within each arm and compared between the arms using a log-rank test. The progression-free survival rates at 3 years and 5 years will be estimated in each arm.

16.32 Time to any therapy (TTNT) is defined as the time from registration to the date of initiation of any treatment for follicular lymphoma. The distribution of time to any therapy will be estimated using the method of Kaplan-Meier within each arm and compared between the arms using a log-rank test. The percentage of patients free of any therapy at 3 years and 5 years will be estimated in each arm.

16.33 Time to chemotherapy (TTC) is defined as the time from registration to the date of initiation of chemotherapy for follicular lymphoma. The distribution of time to chemotherapy will be estimated using the method of Kaplan-Meier within each arm and compared between the arms using a log-rank test. The percentage of patients free of chemotherapy at 3 years and 5 years will be estimated in each arm.

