For all statistical analyses, p-values <0.05 will be considered statistically significant. For interpreting the clinical significance of effects will be evaluated using the FACT cut-offs described above as well as using Cohen's cut-offs (37): <0.20 =trivial; $0.20-0.50$ =small; $0.50-0.80$ =moderate; and >0.80 =large.

16.5 Data & Safety Monitoring:

- 16.51 The principal investigator(s) and the study statistician will review the study at least twice a year to identify accrual, adverse event, and any endpoint problems that might be developing. The Mayo Clinic Cancer Center (MCCC) Data Safety Monitoring Board (DSMB) is responsible for reviewing accrual and safety data for this trial at least twice a year, based on reports provided by the MCCC Statistical Office.
- 16.52 Adverse Event Stopping Rules (these rules apply to Arm A and Arm B independently): Both Arms A (rituximab) and B (Zevalin) are commercial agents used at the FDA-approved dose with standard CBC and bone marrow criteria. Since the doses are the same, we do not expect any difference in the toxicity profile as described in the label. We note that the Adverse Event Stopping Rule may be adjusted in the event of either (1) the study re-opening to accrual or (2) at any time during the conduct of the trial and in consideration of newly acquired information regarding the adverse event profile of the treatment(s) under investigation. The study team may choose to suspend accrual because of unexpected adverse event profiles that have not crossed the specified rule below.

In our previous study of single-agent rituximab for untreated FL(10), we observed 14% grade 3,4 AEs. In previous Zevalin studies for untreated FL (14) there was, as expected, 15% grade 3 and 17% grade 4 (total 32% grades 3,4) neutropenia that was reversible. There was no grades 3,4 non-hematologic toxicity. These toxicities, if they occur, do so within 12 weeks for both Arms A and B. Accrual will be temporarily suspended to both arms if at any time we observe events considered at least possibly related to study treatment (i.e., an

adverse event with attribute specified as “possible”, “probable”, or “definite”) that satisfy either of the following:

- if 3 or more patients in the first 12 treated patients experience a grade 4 or higher non-hematologic adverse event at least possibly related to treatment.

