- if after the first 12 patients have been treated, 25% of all patients experience a grade 4 or higher non-hematologic adverse event at least possibly related to treatment.

We note that we will review grade 4 and 5 adverse events deemed “unrelated” or “unlikely to be related”, to verify their attribution and to monitor the emergence of a previously unrecognized treatment-related adverse event.

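### The second adverse-event stopping bullet in 16.52 counts patients still inside the 12-week toxicity window as event-free, and its 25% boundary for Arm B is not reconciled with the Zevalin experience cited beside it

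*Combined protocol and SAP*

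**What the plan says.** Section 16.52 sets the only numeric safety boundary. It counts grade 4 or higher non-hematologic events at least possibly related to treatment. It is checked continuously ("Accrual will be temporarily suspended to both arms if at any time we observe events considered at least possibly related to study treatment") and works by arm: "these rules apply to Arm A and Arm B independently". There are two bullets:

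- First 12 patients: "if 3 or more patients in the first 12 treated patients experience a grade 4 or higher non-hematologic adverse event at least possibly related to" [the assigned therapy].
- Thereafter: "if after the first 12 patients have been treated, 25% of all patients experience a grade 4 or higher non-hematologic adverse event". No minimum follow-up is required of the patients counted.

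The background rates in the same section are "In our previous study of single-agent rituximab for untreated FL(10), we observed 14% grade 3,4 AEs" for rituximab, with no split by type or grade, and for the cited Zevalin studies 32% grade 3-4 neutropenia together with "There was no grades 3,4 non-hematologic toxicity". On timing: "These toxicities, if they occur, do so within 12 weeks for both Arms A and B". Section 16.25 adds "The anticipated accrual rate is 4 patients per month". Section 16.24 caps enrolment at 128, and Section 16.2 allocates 1:1, so an arm holds up to 64 patients.

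The section gives no reason for 25%, no rate regarded as unacceptable, and no probability that the rule triggers.

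**The concern.** A patient treated last week has had almost no chance to show a toxicity that may take up to 12 weeks, but enters the second bullet's denominator at full weight. Events arrive late and denominators arrive at once, so while accrual continues the running percentage sits below the rate it is meant to track. The shortfall is largest early in an arm, when a suspension would protect the most future patients.

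The second matter is the height of the boundary in Arm B. A 25% limit for grade 4-5 related non-hematologic events stands in the same paragraph as a cited experience of none at grade 3-4. These patients are candidates for observation (3.14), and the hypothesis in 1.3 calls the treatment low in toxicity. Without stated trigger probabilities, neither the DSMB nor a site can tell what the rule would detect.

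**Working it through.** **Inputs.** Accrual 4 per month over two arms, so 2 per arm per month (16.25). Window 12 weeks = 12/4.345 = 2.76 months (16.52). Maximum 64 per arm (16.24, 1:1). Boundaries 3 of 12, then 25% (16.52). Two inputs are assumptions because the plan does not give them: the true event rate (shown from 5% to 30%) and event timing within the window (uniform, with all events at week 12 as the extreme). The 12 weeks are taken to run from first treatment and to apply to the events the rule counts.

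**Plan's own figure.** There is no operating characteristic to reproduce. The two bullets agree with each other: 3/12 = 25%.

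**Step 1, patients inside the window.** 2 x 2.76 = 5.5 per arm. As a share of those treated: 5.5/12 = 46%; 5.5/64 = 9%.

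**Step 2, direction of the bias.** With uniform timing, patients in the window have on average shown half of their eventual events. With n treated and true rate p, the expected count is p(n - 5.5/2), so the written percentage averages about p(1 - 2.75/n): 0.77p at n = 12, 0.86p at n = 20, 0.96p at n = 64.

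The alternative count leans the other way, because patients in the window enter it only if they have had an event. At n = 20 and p = 20%:

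- Expected events: 0.20 x 17.25 = 3.45.
- As written: 3.45/20 = 17%.
- Alternative: denominator 14.5 + 0.20 x 2.75 = 15.05, giving 3.45/15.05 = 23%.

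**Step 3, first bullet.** P(X >= 3) for X binomial(12, p) is 2.0% at p = 5%, 11.1% at 10%, 26.4% at 15%, 44.2% at 20%, 60.9% at 25% and 74.7% at 30%. Its denominator is fixed and it counts those 12 patients' events whenever they occur, so the window does not dilute it.

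**Step 4, whole rule for one arm.** Simulation: Poisson accrual at 2 per month, 64 patients, a check at every event. The alternative second bullet counts only patients with 12 weeks completed or a qualifying event, and is applied once at least 12 such patients exist.

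| True rate | As written, uniform | Alternative, uniform | As written, all at week 12 | Alternative, all at week 12 |
|---|---|---|---|---|
| 5% | 1.9% | 2.8% | 2.0% | 2.2% |
| 10% | 11-12% | 16-18% | 11.5% | 13.7% |
| 15% | 31% | 43% | 29% | 35% |
| 20% | 57% | 70% | 54% | 63% |
| 25% | 82% | 89% | 79% | 85% |
| 30% | 95% | 98% | 94% | 96% |

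**Step 5, how much of the gain is bias correction.** Weighting each patient in the window by the fraction of the 12 weeks completed, instead of leaving out those without an event, gains only about 1-4 points over the written rule. The rest of the gain in the uniform columns comes from the upward lean shown in step 2.

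**The case against.** The strongest reply is that the denominator matters little and other safeguards fill the gap. Much of this stands. The first bullet is unaffected, the share of patients in the window falls to 9% by full enrolment, and low sensitivity at true rates of 5-10% comes almost entirely from the height of the boundary. Section 16.52 also lets the study team suspend accrual for an unexpected profile below the boundary and lets the rule be adjusted at any time. The DSMB reviews safety at least twice a year (16.51), and adverse events enter any decision to terminate the study (16.23). None of these is numeric, however, and a half-yearly review does not replace a trigger meant to act at any time.

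Four stronger readings are tempting, and the documents do not support them:

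- *The rule rarely triggers when it should.* The plan names no rate at which it should trigger, and the rule fires in about 80% of arms at a true 25% and about 95% at 30%.
- *The plan expects none of these events.* The zero is an observation from earlier Zevalin studies. Rituximab's 14% is unsplit, so Arm A's expected rate is unknown, and Section 15 lists severe infusion reactions for both regimens.
- *Related deaths would go unnoticed.* Two among the first 12 patients would not reach the numeric line, but 10.4 and 10.52 provide for expedited reporting of deaths within 24 hours.
- *Neutropenia is unmonitored.* It lies outside the rule, but 16.52 calls it expected and reversible, blood counts follow Zevalin (4.0), neutrophils are graded at each evaluation (10.6), and the DSMB receives safety data.

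**Conclusion.** The concern holds in two limited parts.

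First, the second bullet's denominator is inconsistent with the plan's own 12-week statement and biases the observed percentage down, by about a quarter of the true rate near 12 treated patients and about 4% of it at 64. Restricting the count gains roughly 5-6 points of trigger probability at a true 10% and 12-13 points at 15-20% under uniform timing. The gain is about 2 to 9 points over the same range if every event falls at week 12. These figures rest on the assumed timing, steady accrual of 2 per arm per month, 64 treated per arm and the minimum of 12 countable patients. Part of the gain is the alternative count's upward lean and not removal of bias.

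Second, for Arm B the 25% boundary and the cited Zevalin experience stand side by side without reconciliation, and no trigger probabilities are given. That is a gap in justification. It does not show that 25% is wrong, and it does not extend to Arm A.

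**What to change.** In the second bullet of 16.52, define the patients counted as those who have completed 12 weeks from first treatment or have already had a qualifying event, and state how many such patients are needed before the bullet applies (the figures above use 12; without a minimum, small early denominators would trigger more often). Leave the first bullet's count as it is. If the sponsor wants to avoid the upward lean, a follow-up-weighted denominator is an alternative, with a smaller gain.

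Also in 16.52, reconcile the 25% boundary with the cited Zevalin experience for Arm B, and tabulate the rule's trigger probabilities over a range of true rates for each arm. The threshold itself is for the sponsor and DSMB to justify.

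The cost is protocol wording and a short simulation; no new data are needed. The downside is a slightly higher chance of a temporary pause. At a true 5% in an arm it rises from 1.9% to about 2.8%. Because either arm suspends both, if both arms were at 5% and independent it would rise from 1 - 0.981² = 3.8% to 1 - 0.972² = 5.5% of trials.
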